This raises the question whether there are simple analyses that throw more appropriate light on the psychometrics of using the questionnaires to measure individual change than do the conventional explorations of psychometric quality of multi-item questionnaire measures for cross-sectional comparisons between people. This will be explored (details in the PPDAC "A" section: analyses, below).

- iii. As most existing data on the well-being and mental health problems of this age group are from student samples, a primary focus will be on differences between a student and a non-student sample both at baseline and subsequently through the year.
- iv. How much do scores on the dependent measures (CORE-OM, EQ-5D-3L and EQ-VAS, see registration) vary across the seven time points and is there evidence that the level of variation varies across the sample, i.e. that temporal stability is not a consistent parameter but show strong individual differences? Analyses of the CORE-OM will consider the non-risk and risk scores only (but see "supplementary analyses").
- v. Does baseline group, student vs. non-student, appear to relate to the dependent variables? Do other demographic predictors relate to the dependent variables? Recognising that "the dependent variables" will have temporal variation this will be divided into two sets of analyses:
 - 1. Using baseline scores only
 - 2. Analysing the full change data (more details below):
 - a. Testing for difference in any systematic linear trend over the seven time points.
 - b. Against within-participant SD of the scores.
 - c. Against highest and lowest within-participant difference from baseline.
- vi. What levels of and changes in stressors/life events (LE) do participants report on the novel "What's going on?" (WGO) measure?
- vii. Is there evidence of systematic relationship between stress and dependent variable scores within-participant over time?
- viii. Given the inevitably non-random nature of the sampling creating the dataset this will be compared with the most recently available census data

from Quito for this age group to see how much the sample differs from the census data where comparable variables are present in the census data.

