Some participants will probably change group during the year though these will probably be less numerous than "students-who-also-hold-jobs". Due to the timing of the data collection, students are probably more likely to terminate their courses during the year than are non-students to start a degree. Here again, sensitivity analyses will be conducted recomputing the analyses (a) omitting participants who change group at any point in the year and (b) omitting only those changing group whose change comes less than half way through the year and (c) reallocating those who change group to the group they fall in for more than half the year. However, the expectation is that the numbers changing group will be small and the impacts on the ITT findings small or negligible.

Recognising that these dependent variables have temporal variation and this variation is likely to be complexly patterned across the entire sample, the following analyses will be reported for the ITT baseline group comparison and the sensitivity analyses noted above.

- Group difference against mean scores across all non-missing scores from all seven occasions. This extends the analyses of baseline group differences and entirely ignores change over time.
- Group difference in linear trend over the time points using multi-level modelling (MLM). This allows a trend to be fitted both as a fixed effect whose interaction with predictors can be tested, i.e. assuming a single within-group population mean, and then also allowing a free effect, i.e. allowing that linear trend against time may vary between individuals. The MLM provides an individual (free) linear slope if scores at least two time points exist. However, sensitivity checks on effects of missingness will be added by restricting to sequentially larger numbers of time points.
- Group differences in within-participant SD of the scores (wpSD).
- Group differences in within-participant score difference from baseline (wpMaxChange).
- Group differences in within-participant score range (wpScoreRange).
- Do other demographic predictors relate to the dependent variables? Same methods as for group differences.

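### The only group comparison that uses the order of the seven waves is a straight line, so a non-linear student/non-student difference through the year could be missed or distorted

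*SAP*

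**What the plan says.** Question iii of the SAP's Problem section makes a primary focus of "differences between a student and a non-student sample both at baseline and subsequently through the year". Question v.2.a turns the time course into "Testing for difference in any systematic linear trend over the seven time points". The Change analyses section repeats this as "Group difference in linear trend over the time points using multi-level modelling (MLM", fitted first with a common slope and then "allowing that linear trend against time may vary between individuals". No wave factor, curvature, calendar-month or term variable is named.

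The sentence that introduces this list says that "this variation is likely to be complexly patterned across the entire sample".

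The slope is not the only planned comparison of change. The same list has a group comparison of the mean over all occasions and three of within-participant change: "Group differences in within-participant SD of the scores (wpSD", "Group differences in within-participant score difference from baseline (wpMaxChange" and wpScoreRange. The section also plans change on dichotomised scores by baseline group, rates of reliable change, and plots of all change scores with central values and CIs.

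**The concern.** A difference through the year need not be a difference in slope. Follow-up lasts one year, and only one group is studying. If students' scores rose and fell within the year, a straight line would describe that poorly. The fitted slope would also depend on where in the pattern baseline happened to fall. The same student course could then give a group-by-time slope near zero, or a clear slope in either direction. The remaining indices collapse the seven waves into one number per person, so they cannot show when the groups separate.

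**Working it through.** **Inputs from the SAP.** One year of follow-up, seven occasions, a linear trend in time. The SAP gives no effect size, SD or sample size for this comparison, so there is no stated figure to reproduce.

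**Assumptions.** Waves at t = 0, 2, ..., 12 months; complete data; non-students flat; students on a sinusoid of amplitude A with no net yearly change, period 12 or 6 months.

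**Slope from a cycle.** Centre time at mid-year: u = -6, -4, -2, 0, 2, 4, 6, so the sum of u² is 112. Slope = Σuy / 112, and yearly change = 12 × slope. The part of the cycle symmetric about mid-year adds nothing, so the slope is zero when a 12-month cycle has baseline at a peak or trough. It is largest when baseline lies midway between them.

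- 12-month cycle, largest case: y = ±0.866A at u = ±2, ±0.866A at u = ±4, and 0 at ±6. Σuy = 2(2 × 0.866 + 4 × 0.866)A = 10.39A. Yearly change = 12 × 10.39A / 112 = 1.11A. Share captured = (10.39² / 112) / (4 × 0.75) = 0.964 / 3 = 0.32. Over all phases: -1.11A to +1.11A, and 0% to 32%.
- 6-month cycle, largest case: y = ±0.866A at u = ±2 and ∓0.866A at u = ±4. Σuy = 2(2 × 0.866 - 4 × 0.866)A = -3.46A. Size of yearly change = 12 × 3.46A / 112 = 0.37A. Share captured = (3.46² / 112) / 3 = 0.036.

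With A = 0.2 SD, the largest false group difference in yearly change for a 12-month cycle is 1.11 × 0.2 = 0.22 SD.

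**Simulation.** 12-month cycle in students only, A = 0.2 SD, 200 per group, total SD 1, intraclass correlation 0.6, complete data, two-sided 5%. There were 600 runs per setting (1,000 for the no-cycle row).

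| Baseline falls | Mean 12-month slope difference | Slope test rejects | Group-by-wave test (6 df) rejects | wpSD comparison rejects |
|---|---|---|---|---|
| at a peak | 0.00 SD | 7% | about 100% | 20% |
| midway (either direction) | -0.22 or +0.22 SD | 86-88% | 99% | 14-15% |
| no cycle (A = 0) | 0.01 SD | 5% | 6% | 5% |

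With A = 0.1 SD and 100 per group, the group-by-wave test rejects only 24-34%.

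**Does staggered entry cancel it?** The design was registered on 22/10/20, before data collection, and the SAP of 28/2/22 was written just before collection ended. If everyone had a full year, baselines fell within 129 days, about 4.2 months. An even spread of ±2.1 months leaves a factor sin(x)/x with x = 2π × 2.1 / 12 = 1.10, that is 0.891 / 1.10 = 0.81, so about 81% of the false slope remains. Simulated with ±2 months: -0.18 SD, slope test 70%, group-by-wave 95%. With entry spread evenly over a whole year the false slope vanishes (slope test 6%). The group-by-wave test then sees nothing either (6%), and only a calendar term could show the cycle.

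**Other indices.** A pure 12-month cycle gives wpSD of 0.71A to 0.80A and a range of 1.73A to 2.00A at whole-month phases, so these indices do respond to it. However, the wpSD group comparison rejects only 9-25% at A = 0.2 SD and 25-80% at A = 0.3 SD (100 to 300 per group). wpMaxChange also depends on phase, running from -2.00A to +2.00A.

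**The case against.** Several stronger readings are tempting, and the SAP does not support them.

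- A reader might infer that change is compared between groups only by slope. It is not: three within-participant change indices, dichotomised change, reliable change and plots are also planned. The shares of 32% and 4% describe the slope alone, not the whole set of analyses.
- A reader might infer that the SAP itself expects an academic cycle, because it says that "Due to the timing of the data collection, students are probably more likely to terminate their courses during the year". That sentence concerns participants who change group, for which sensitivity analyses are planned. It does not say that timing affects scores. The cycle, its amplitude, its restriction to students and the wave spacing are all assumptions here, and 0.22 SD is the worst phase.
- A reader might infer that time is counted from each person's own baseline. The SAP says only time and time points, and refers design details to the registration.
- A reader might infer that a null slope will be reported as no difference in change. Nothing says so. The SAP calls the study exploratory, prefers estimation with CIs to testing, and commits itself to visualising data, reporting several models and interpreting modestly.

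A linear model does answer the narrow question v.2.a. Making a 6-df test the main test would also impose a hierarchy that this plan does not have. These objections stand. They leave one gap: question iii is wider than a slope, and no other planned analysis models the timing of a group difference.

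**Conclusion.** The point holds in a limited form. The only time-ordered group model is linear, although question iii asks about differences through the year and the SAP expects complex patterning. If students followed a 12-month cycle with no net change, seven equally spaced waves would give a fitted yearly change between -1.11A and +1.11A by phase alone, with 0% to 32% of the cyclic variation captured. For a 6-month cycle the figures are up to 0.37A and at most 4%. Whether such a cycle exists, and how large A is, cannot be learned from the SAP, so the actual effect is unknown. This is a cheap improvement, not an error that invalidates the planned slope analysis.

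**What to change.** Keep the linear slope and add three things to the Change analyses section:

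1. The same multi-level model with wave as a categorical factor and a group-by-wave interaction, keeping the random individual effects. Report it as the estimated group difference with a 95% CI at each wave.
2. A sensitivity analysis with calendar month, or academic term, of each completion, where completion dates allow.
3. A statement that a slope will not be interpreted as improvement or worsening if the group-by-wave pattern is clearly non-linear.

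The cost is a few lines of text and one variant of a model already planned. The group-by-wave comparison has less power than the slope if the true difference is linear, and late-wave contrasts will be less precise because the SAP expects non-response to grow over waves 2 to 7. Keeping the slope covers the first drawback. The SAP allows marked amendments before the affected data are analysed. If added later, the model should be labelled post hoc under the SAP's own rule.

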- In this epistemological position this study is best regarded as a well powered but exploratory test of the methods contributing a substantial, but tentative, body of new knowledge.
- The data are largely quantitative and the approach largely statistical within a statistical tradition of (Abelson, 1995; Spiegelhalter, 2019). We also follow the principles of (Wagenmakers et al., 2021, 'Seven steps toward more transparency in statistical practice') specifically:
 - (1) visualizing data;
 - (2) quantifying inferential uncertainty;
 - (3) assessing data preprocessing choices;
 - (4) reporting multiple models;
 - (6) interpreting results modestly; and
 - (7) sharing data and code.

Their fifth step, involving multiple analysts is beyond our resources but we welcome offers from others to reanalyse our data, ideally in collaboration but of course our making the data and code available publicly makes it possible for anyone to reanalyse our data. Particular reference to these steps are noted against particular aspects of our analyses below.

- Some elements are frankly exploratory and pathfinding: mainly the quantitative and qualitative data from the "What's Going On?" (WGO, see registration and protocol) and their relationship with other variables. We are particularly careful to present these as such and not to overclaim for them (Wagenmakers et al., 2021, steps 1, 2, 4 and 6).
- In general the statistical position is descriptive and based on estimation rather than formal null hypothesis significance testing (NHST) and we use confidence intervals (CIs) to understand the probable impacts of sample size on precision of estimation of population parameters. Where statistical tests are used, they aim to give a pragmatic indication that non-random effects exist, not to give strong assertions that "x is a statistically significant effect" but, with the CIs, to help disentangle seemingly systematic effects from random ones. (Wagenmakers et al., 2021, steps 2, and 6)
- We recognise that the sample is not a random one so caution will be exercised in any generalisations to the wider population (Wagenmakers et al., 2021, steps 2 and 6).
- We recognise that there will be incomplete responding and that a small proportion of participants may cross from one baseline group, i.e. students or non-students, to the other group. The impacts of these issues will be explored (Wagenmakers et al., 2021, steps 2, 3, 4 and 6).

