 - With hindsight and having conducted analyses along these lines we are aware that there are many other ways of exploring these complexities in survey data and would particularly welcome offers from data analysts to explore other methods of exploration of these issues in this baseline dataset.
 - Baseline non-participation will be reported to the extent that the opportunistic recruitment process allows though this can only be in terms of potential number of students who might have opted into the study and then in terms of the numbers who start the online data collection but opt out before giving usable data.
 - For the CORE-OM and EQ-5D-3L internal reliability and factor analysis will be conducted (but not expecting neat factor structures). In addition, convergent validity correlations between the two measures, and with the EQ-VAS, will be reported, as usual with 95% CIs.
 - Distributions of CORE-OM, EQ-5D-3L and EQ-VAS scores and of WGO scores will be reported with CIs for centiles.
 - Baseline associations between those three dependent variables and the WGO scores will be reported with scattergrams and smoothed LOESS

regression lines and CIs.

- **Change analyses**

- Patterns of post-baseline missingness will be reported. These will almost certainly show a preponderance of simple attrition: i.e. increasing non-response in waves 2 to 7, however, other patterns are also likely to be observed. As there are 64 possible further completion patterns (2^6) the missingness will be analysed in terms of simple dichotomy of "all completed" versus "at least one missing" and in terms of the total number of completions (1 to 7). These will be analysed against baseline demographic and dependent variable scores for evidence of any of these variables showing systematic associations with missingness. The associations will be reported testing against an alpha of .01 as in the baseline analyses but also with CIs for the associations.

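### Re-fitting the group-trend model in participants with ever more completed waves selects on retention, so neither a stable nor a drifting sequence shows whether dropout has biased the trend

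*SAP*

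**What the plan says.** All of this is in the SAP, and mostly in the Change analyses part of the PPDAC section A (Analyses).

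- **Trend model.** The group difference in linear trend is to be estimated by multi-level modelling, first with a common slope within group and then with slopes that vary between individuals. The text notes that "The MLM provides an individual (free) linear slope if scores at least two time points exist" and goes straight on to say that "sensitivity checks on effects of missingness will be added by restricting to sequentially larger numbers of time points".
- **Expected missingness.** On the patterns of missing waves: "These will almost certainly show a preponderance of simple attrition: i.e. increasing non-response in waves 2 to 7". No rate is given.
- **Missingness analysis.** Completion is summarised as all waves versus at least one missing, and as the number of completions. "These will be analysed against baseline demographic and dependent variable scores for evidence of any of these variables showing systematic associations with missingness". Further, "The associations will be reported testing against an alpha of .01 as in the baseline analyses", with confidence intervals.
- **General commitment.** Under Epistemological and methodological position, incomplete responding and group switching are acknowledged, and "The impacts of these issues will be explored". No method is named there.

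The SAP states no missing-data assumption for the multi-level model and plans no analysis of departures from one. Its other sensitivity analyses, on students with jobs and on people who change group, do not concern missingness.

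**The concern.** The number of waves a person completes is a result of the dropout process and is known only after baseline. A correctly specified likelihood model on every available score gives a valid trend when dropout depends on scores already observed. Each restriction to people with at least k waves gives up some of that protection, and at k = 7 the analysis is of completers only. The check therefore compares a better-protected estimate with less-protected ones. It varies nothing about the scores that were not seen, which is where bias from dropout would lie.

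Differences between students and non-students through the year are named as a primary focus (specific question iii, with the linear trend at v.2.a). The SAP applies the same methods to the other demographic predictors, so the check recurs. If its output is taken at face value, a biased trend could look robust and a correct one could look fragile.

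**Working it through.** The SAP has no figure to reproduce here: it gives no sample size, variances, attrition rate or effect size for the trend. The check was a large-sample simulation, so that the results show bias and not noise.

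**Assumed inputs (none from the SAP except the seven waves).** Time runs from 0 to 1 over the seven waves. Random-intercept SD is 0.8, random-slope SD 0.7 and residual SD 0.5. The baseline SD is then √(0.8² + 0.5²) = √0.89 ≈ 0.94, so a slope difference is roughly in baseline SDs per year. The slope difference is 0.2 before any worsening after dropout. There are 150,000 people per group, and about 44% to 53% complete all waves in the scenarios tabled.

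**Model.** y = intercept + time + group + group × time, with random intercept and slope, fitted by maximum likelihood. It was fitted to all available scores, then to people with at least 2, 3, …, 7 waves. The truth is the same model fitted to the data with nothing missing.

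| Dropout process | Truth | All data | At least 2 waves, up to 7 |
|---|---|---|---|
| Completely at random | 0.202 | 0.202 | 0.200 to 0.202 throughout |
| On last observed score, same in both groups | 0.194 | 0.194 | 0.196 falling to 0.176 |
| On last observed score, one group only | 0.194 | 0.193 | 0.237, 0.233, 0.205, 0.164, 0.113, 0.054 |
| Same, weaker | 0.201 | 0.199 | 0.217, 0.218, 0.206, 0.184, 0.153, 0.114 |
| Leavers in one group worsen by 0.5 after leaving | 0.434 | 0.201 | 0.198 to 0.201 throughout |
| On current unseen score, one group only | 0.204 | -0.028 | 0.013, 0.035, 0.042, 0.031, 0.008, -0.027 |
| On own slope, one group only | 0.201 | -0.105 | -0.106 falling to -0.192 |
| On change from baseline, one group only | 0.199 | -0.028 | -0.038 falling to -0.210 |

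Reading the table:

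1. **Biased and flat.** In the fifth row the bias is 0.201 - 0.434 = -0.233, and the sequence spans 0.003. In the sixth row the bias is -0.232 and the whole sequence, all-data fit included, spans 0.070.
2. **Unbiased and drifting.** In the third row the all-data bias is 0.193 - 0.194 = -0.001, while the sequence moves by 0.054 - 0.237 = -0.183.
3. **Biased and drifting.** In the last two rows the all-data fit is biased by -0.306 and -0.227, and the restricted fits end further from the truth.
4. **Neither.** Under completely random dropout, and nearly so when dropout on observed scores works alike in both groups, there is little to see. In a smaller run with dropout on the current unseen score, alike in both groups, the truth was 0.204, the all-data fit 0.172 and the sequence 0.165 to 0.180 (standard errors about 0.011 to 0.013). That bias of about -0.03 compares with -0.23 when the process acts in one group only.

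**Second set of assumptions.** True difference zero, intercept variance 0.6 plus residual variance 0.4 (baseline SD 1), slope SD 0.12 per wave, about 40% completing, dropout related to distress in one group only. Figures are year-long differences in baseline SDs, for log-odds of 0.5 and 1.0.

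- Dropout on own slope (all-data fit biased): -0.19 moving to -0.28, and -0.32 moving to -0.43.
- Dropout on last observed score (all-data fit correct): 0.00 moving to -0.07, and 0.00 moving to -0.13.
- The biased and the unbiased case drift by similar amounts (0.09 and 0.11 against 0.07 and 0.13), so the drift does not tell them apart.

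**A possible replacement, tested on the same footing.** Averaging person slopes over dropout patterns works when dropout depends on the slope. When dropout depends on the last observed score, it gives about +0.45 SD at log-odds 0.5, and +0.89 to +0.98 SD at 1.0 across separate runs. The true value is zero and the all-data model gives 0.00.

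**The case against.** **The plan is modest.** It calls the study exploratory, prefers estimation to testing, and commits to reporting several models and interpreting them cautiously. It sets no rule for reading the restricted fits. A reader might infer that a flat sequence will be reported as proof of robustness; the text does not say so. This lowers the stakes. The SAP does, however, present these fits as checks on the effects of missingness, and they cannot serve as that.

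**It is not the only work on missingness.** The Change analyses also relate completion to baseline demographics and baseline scores, with confidence intervals. This stands: the restricted fits are only the sole check that re-estimates the trend. The other analysis is descriptive, and being limited to baseline variables it cannot detect dropout driven by later or unseen scores.

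**The main model is sound.** Nothing in the SAP excludes baseline-only participants from the multi-level model, and the restriction is an addition to it. This also stands, so keeping the all-data fit as the reference only makes the existing plan explicit.

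**The failures need group-specific dropout.** They appear when the dropout process differs between students and non-students. The SAP gives no evidence on this either way. With a shared process the check does little harm, but then there is little bias for it to find.

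**Conclusion.** The point holds in a limited form: the check is not diagnostic of dropout bias. It conditions on retention, and its result can be flat with a bias of -0.23 or can drift by -0.18 with no bias.

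A reader might infer a firm rule, that stability signals bias and drift signals its absence. That is not supported. Several informative dropout processes produce both bias and drift, and completely random dropout produces neither.

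The argument about selection does not depend on the assumed values. The sizes do, because the SAP supplies no sample size, variances or attrition rate. They also assume a dropout process that differs between the groups. The conclusion takes the phrase about larger numbers of time points to mean participants with at least k completions, which is how it reads after the sentence on two time points.

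**What to change.** 1. State that the multi-level model on all available scores, including those of baseline-only participants, is the reference analysis, and that it assumes data missing at random given the observed scores and model terms.
2. Keep the fits by minimum number of waves if wanted, but label them descriptive results in people who stayed, not a check on missingness.
3. Add a delta-adjusted multiple imputation. Impute under missing at random from a model that matches the multi-level model, then shift the unobserved scores after dropout over a stated range, separately for students and non-students. Zero shift in both groups should agree closely with the reference fit. Report the estimate and interval across the range, and the shift at which the conclusion changes. Since the SAP works by estimation, define that beforehand, for instance as the shift at which the estimate changes sign or its interval starts or stops including zero.
4. Do not use a simple average of person slopes over dropout patterns as the replacement, given its bias when dropout depends on the last observed score.

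**Cost.** SAP wording and a modest amount of R code; no new data. The range of shifts has to be chosen and justified. The SAP's own amendment procedure covers the change, and version 2.2 is dated before any inspection of the change data. If those data have since been examined, mark the added analysis as post hoc.
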